8.1.4 Specific Safety Measures

8.1.4.1 Hemoglobin decrease

For a hemoglobin decrease of >1.5 g/dL from baseline during the study, repeat hematology studies and reflexive evaluation of reticulocyte count will be performed. The subject's past medical history, concomitant medications (including over the counter drugs and herbal supplements), and any recent symptoms (e.g., bleeding, shortness of breath, fatigue) will be reviewed to determine a potential etiology and make a clinical assessment of the significance of the finding.

8.1.4.2 Creatinine increase

If, at any visit, a creatinine increase >0.3 mg/dL (27 μ mol/L) from baseline or a GFR decrease of >15 mL/min from baseline is observed, a repeat chemistry will be performed. The subject's past medical history, concomitant medications (including over the counter drugs and herbal supplements), and any recent symptoms (e.g., fatigue, malaise, polyuria/oliguria, or palpitations) will be reviewed to determine a potential etiology and make a clinical assessment of the significance of the finding.

During the study, clinically significant abnormal results in NGAL will be used as a means of identifying subjects who have unremarkable creatinine/BUN values at the time of assessment but may require additional or closer/follow-up monitoring of renal studies.

8.1.4.3 Possible muscle and liver injury

For muscle injury, CK, hepatic, and renal function laboratory data will be integrated with myopathy signs and symptoms. For management of CK elevations $>3 \times$ ULN, refer to [Appendix E](#). For liver injury, laboratory data will be integrated with hepatic signs and symptoms. Alanine aminotransferase increases $>2 \times$ ULN with symptoms of hepatitis or $>3 \times$ ULN with or without symptoms of hepatitis will be evaluated and managed according to guidelines.

8.2 Serious Adverse Events

An adverse event or adverse reaction is considered serious if, in the view of either the Investigator or Sponsor, it results in any of the following outcomes:

- Death;
- A life-threatening adverse event;
 - NOTE: An adverse event or adverse reaction is considered “life-threatening” if, in view of either the Investigator or Sponsor, its occurrence places the subject at immediate risk of death. It does not include an event that, had it occurred in a more severe form, might have caused death.
- Requires hospitalization or prolongation of existing hospitalizations;
 - NOTE: Any hospital admission with at least one overnight stay will be considered an inpatient hospitalization. An emergency room visit without hospital admission will not be recorded as a SAE under this criterion, nor will hospitalization for a procedure scheduled or planned before signing of informed consent. However, unexpected complications and/or prolongation of hospitalization that occur during elective surgery should be recorded as adverse events and assessed for seriousness. Admission to the hospital for social or situational reasons (i.e., no place to stay, live too far away to come for hospital visits) will not be considered inpatient hospitalizations.
- A persistent or significant disability/incapacity or substantial disruption of the ability to conduct normal life functions;
- A congenital anomaly/birth defect; or
- An important medical event.

- NOTE: Important medical events that may not result in death, be life-threatening, or require hospitalization may be considered an SAE when, based upon appropriate medical judgment, they may jeopardize the subject and may require medical or surgical intervention to prevent one of the outcomes listed in this definition. Examples of such medical events include allergic bronchospasm requiring intensive treatment in an emergency room or at home, blood dyscrasias or convulsions that do not result in inpatient hospitalizations, or the development of drug dependency or drug abuse.

8.3 Serious Adverse Event Reporting

All observed or volunteered SAEs regardless of treatment group or suspected causal relationship to the study drug will be reported as described below. If a SAE occurs, the sponsor or designee is to be notified within 24 hours of awareness of the event by the investigator or designee.

All SAEs and follow-up information must be reported to the sponsor or designee within 1 business day or 24 hours of awareness of the event as required by your local requirements by emailing or faxing a completed SAE report form to the following:

Safety Contact Information: PI [REDACTED]

Facsimile: PI [REDACTED]

E-mail: PI [REDACTED]

In particular, if the SAE is fatal or life-threatening, notification to the sponsor or designee must be made immediately, irrespective of the extent of available AE information.

This timeframe also applies to additional new information (follow-up) on previously forwarded SAE reports, initial and follow-up reporting of exposure in utero (EIU) cases, and any SAEs that the Investigator considers related to study drug occurring after the 30-day follow-up period.

The Investigator must continue to follow the patient as medically necessary until the SAE has subsided or until the condition becomes chronic in nature, stabilizes (in the case of persistent impairment), or the patient dies.

In the rare event that the investigator does not become aware of the occurrence of a SAE immediately (eg, if an outpatient study subject initially seeks treatment elsewhere), the investigator is to report the event within 24 hours after learning of it and document the time of their first awareness of the SAE.

8.4 Pregnancy Reporting

For investigational products within clinical studies, an Exposure In Utero occurs if:

- A female becomes, or is found to be pregnant after receiving the study drug (eg, after Study Day 1).

If a patient participating in the study becomes pregnant during their participation in the study or within 30 days of discontinuing study drug, the Investigator must report the pregnancy to PI [REDACTED] within 24 hours of awareness on the Exposure In Utero form.

A patient becoming pregnant while on study drug will immediately be withdrawn from the study and early termination study procedures will be performed.

The Investigator will follow the subject until completion of the pregnancy or until pregnancy termination (ie, induced abortion) and notify PI [REDACTED] of the pregnancy outcome. The investigator will provide this information as a follow up to the initial EIU form. The reason(s) for an induced abortion should be specified. If the outcome of the pregnancy meets the criteria for immediate classification as an SAE (i.e., postpartum complication, spontaneous abortion, stillbirth, neonatal death, or congenital anomaly), the Investigator should follow the procedures for reporting SAE(s).

In the case of a live birth, the “normality” of the newborn can be assessed at the time of birth (ie, no minimum follow-up period of a presumably normal infant is required before an EIU form can be completed). The “normality” of an aborted fetus can be assessed by gross visual inspection, unless pre-abortion findings are suggestive of a congenital anomaly.

8.5 Expedited Reporting

The Sponsor will report all relevant information about suspected unexpected serious adverse reactions that are fatal or life-threatening as soon as possible to the Food and Drug Administration (FDA), applicable competent authorities in all the Member States concerned, and to the Central Ethics Committee, and in any case no later than 7 days after knowledge by the Sponsor of such a case, and that relevant follow-up information will subsequently be communicated within an additional 8 days.

All other suspected unexpected serious adverse reactions will be reported to the FDA, applicable competent authorities concerned, and to the Central Ethics Committee concerned as soon as possible, but within a maximum of 15 days of first knowledge by the Sponsor.

The Sponsor will also inform all investigators as required.

Expedited reporting of suspected unexpected serious adverse reactions related to non-investigational medical products (NIMPs) used in this study (e.g., simvastatin, atorvastatin, rosuvastatin, and/or ezetimibe) will not be necessary. Listings of cases related to these NIMPs will be included in the Development Safety Update Report.

8.6 Clinical Laboratory Evaluations

Clinical laboratory evaluations will be collected at the visits shown in the Schedule of Procedures ([Appendix A](#)) and the data captured will be forwarded to the central laboratory for evaluation. Assessments that require a subject to fast will be defined as no food or caloric beverage for at least 10 hours prior to sample collection. Subjects will be permitted to have water ad lib.

Central laboratory results will be provided to the sites, with the exception of the post-randomization lipid values. Laboratory results that appear potentially spurious based on the Investigator’s clinical assessment and review of the subject’s medical history may be repeated for confirmation of the finding. Reassessments of non-qualifying screening labs must be reviewed and approved by the Medical Monitor prior to obtaining the new specimen. The clinical rationale for performing repeat testing of screening assessments should be thoroughly documented.

Standard clinical laboratory evaluations for safety chemistry, coagulation, and hematology will be conducted at all study visits and the Follow-up Visit (only for subjects who had an abnormal

result at Week 12 [or the ET Visit, if applicable] or an ongoing treatment-related adverse event). Clinically significant abnormal creatinine results at Week 12 (or the ET Visit, if applicable) will also be followed-up 2 weeks (± 3 days) after the last dose of study drug in addition to the 4 week (± 3 days) Follow-up Visit. See [Appendix B](#) for a list of clinical laboratory analytes.

At the Pre-Screening Visit, if applicable, fasting LDL-C and TG will be measured. A full fasting lipid panel will be assessed at all other study visits, excluding the Follow-up Visit. Fasting apolipoproteins will be assessed at Day 1, Week 4, Week 8, Week 12, and the ET Visit, if applicable. In addition to these lipid parameters, C hsCRP, SAA, adiponectin, FPG, fasting insulin, and fibrinogen will also be measured at Day 1, Week 12, and the ET Visit, if applicable.

A urine sample for urinalysis will be collected at the Pre-Screening Visit, if applicable, the Screening Visit, Day 1, Week 4, Week 8, Week 12, the Follow-up Visit (only for subjects who had an abnormal result at Week 12 [or the ET Visit, if applicable] or an ongoing treatment-related adverse event), and the ET Visit, if applicable. A urine microscopic examination will be performed when the dipstick result is abnormal (positive for blood, leukocyte esterase, or nitrites). Urine protein:creatinine ratio and albumin:creatinine ratio will be performed at the Screening Visit, Day 1, Week 4, Week 12, the Follow-up Visit (only for subjects who had an abnormal result at Week 12 [or the ET Visit, if applicable] or an ongoing treatment-related adverse event), and the ET Visit, if applicable. Urinary NGAL will be measured at Day 1, Week 4, Week 12, the Follow-up Visit (only for subjects who had an abnormal result at Week 12 [or the ET Visit, if applicable] or an ongoing treatment-related adverse event), and the ET Visit, if applicable.

Tests for HBV, HCV, and HIV will be conducted at the subject's first study visit, either at the Pre-Screening Visit, if applicable, or the Screening Visit.

For women of child-bearing potential only, a serum pregnancy test will be conducted at the Screening Visit, Week 12, and the ET Visit, if applicable. A urine pregnancy test will be conducted at the Pre-Screening Visit, Day 1, Week 2, Week 4, and Week 8.

Thyroid-stimulating hormone will be measured at the subject's first study visit, either at the Pre-Screening Visit, if applicable, or the Screening Visit.

HbA1c will be measured at the subject's first study visit, either at the Pre-Screening Visit, if applicable, or the Screening Visit, Week 12, and the ET visit, if applicable.

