Since LDL-C effects were similar across monotherapy and add-on to stable statin therapy (Figure 1), the groups were combined in an overall analysis.

Figure 1: Pooled Monotherapy (1025-004; 4141001) and Add-On LDL-C Effects to Stable Statin Therapy (1027-018)

Mean percent change and difference from placebo in LDL-C for gemcabene 150 mg, 300 mg, 600 mg, and 900 mg was +3.6 (p=0.4146), -11.1 (p=0.001), -20.2 (p<0.0001), and -20.9 (p<0.0001), respectively. This was supported by a dose-dependent reduction in atherogenic particles (Apo B) statistically different from placebo at gemcabene 300 mg, 600 mg and 900 mg.

The LDL-C efficacy data outlined above supports the 600 mg dose of gemcabene as the optimal dose for LDL-C lowering to further study in Phase 2 in study GEM-301 prior to testing in Phase 3. GEM-301 is designed to determine additional LDL-C lowering and safety of gemcabene 600 mg over 12 weeks on high-intensity and moderate-intensity stable background statin therapy.

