5.3 Randomization and Blinding

Subjects who have completed the Screening Visit and meet all of the inclusion and none of exclusion criteria will be randomized into the study on Day 1. Randomized treatment assignment and randomization numbers will be assigned via IWRS/IVRS. Following randomization, study drug will be dispensed in a double-blind manner. The Sponsor and all clinical site personnel (Investigator, pharmacist, etc.) will be blinded to the treatment group for each subject. Subjects also will be blinded to the treatment they receive.

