9.3 Baseline Definitions

Baseline for a given parameter is generally defined as the last assessment prior to the first dose of the study drug but varies depending on the parameter:

- Baseline for lipids (ie, LDL-C, non-HDL-C, TC, TG, HDL-C and VLDL-C) is defined as the average of the corresponding parameter's last 2 non-missing values between (and including) Screening and pre-dose Day 1. If only 1 value is available, it will be used for baseline.
- Baseline for apolipoproteins (ie, ApoB, ApoA-I, ApoA-II, ApoA-V, ApoC-II, ApoC-III, ApoE, and Lp[a]), inflammatory biomarkers (ie, hsCRP, SAA, adiponectin and fibrinogen), serum C1, fasting insulin, and FPG is defined as the corresponding parameter's last non-missing value between (and including) Screening and pre-dose Day 1.
- Baseline for HbA1c is defined as the value from the first visit (Pre-Screening or Screening Visit).
- Baseline for ECGs, vital signs, body mass index (BMI), weight, and safety laboratory parameters (ie, chemistry, hematology, coagulation, and urinalysis parameters) is defined as the last pre-dose measurement (pre-dose Study Day 1 or before) for the corresponding parameter.
- Baseline Framingham Risk Score for each subject will be computed using the following variables at the following time points: age at the Screening Visit, baseline TC (previously defined), baseline HDL-C, baseline SBP, treatment for hypertension at Day 1, smoking status at Day 1, and diabetes status at the Screening Visit.

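### The rule withholding post-randomization lipid values from sites leaves hsCRP and SAA visible and is unclear on apolipoproteins

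*Protocol*

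**What the plan says.** Protocol 5.3 sets the standard: "The Sponsor and all clinical site personnel (Investigator, pharmacist, etc.) will be blinded to the treatment group" of each subject. Protocol 8.6 contains the only rule found on release of laboratory results: "Central laboratory results will be provided to the sites, with the exception of the post-randomization lipid values". The term for the withheld group is not defined there or elsewhere.

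Section 8.6 goes on to describe the lipid panel and then states: "Fasting apolipoproteins will be assessed at Day 1, Week 4, Week 8, Week 12, and the ET Visit, if applicable". The next sentence opens "In addition to these lipid parameters" and lists hsCRP, SAA and others, ending "adiponectin, FPG, fasting insulin, and fibrinogen will also be measured at Day 1, Week 12, and the ET Visit, if applicable". Appendix A agrees that hsCRP and SAA have no scheduled sample between Day 1 and Week 12.

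Elsewhere, lipids and apolipoproteins are separate groups. The secondary objectives name both. Appendix A gives them separate rows, and its lipid-panel footnote lists six analytes without ApoB. SAP 9.3 uses the same six: "Baseline for lipids (ie, LDL-C, non-HDL-C, TC, TG, HDL-C and VLDL-C) is defined" in one bullet, and apolipoproteins follow in another.

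**The concern.** Lipid results are presumably withheld because a drug-responsive result could hint at the assigned arm. The same reasoning applies to any other marker that the protocol expects the drug to move. Protocol 1.1 reports a marked reduction in hsCRP. Protocol 1.2 reports for ApoB a "dose-dependent reduction in atherogenic particles (Apo B) statistically different from placebo at gemcabene 300 mg, 600 mg and 900 mg". The Day 1 sample is taken before randomization and is released, so a site that receives a later value can work out the subject's own change.

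What is at stake is judgment by site staff. Safety and tolerability are a secondary objective. Relatedness is the investigator's yes/no call (Protocol 8.1.3), and adverse events are collected until the Follow-up Visit (8.1). Under Protocol 6.5 that visit is a telephone call unless there was an abnormal Week 12 or early-termination result or an ongoing treatment-related event. A relatedness call can therefore affect which follow-up safety data are collected.

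The rule also names only sites. The sponsor is to be blinded too, and it determines the Per-Protocol Set before unblinding (SAP 7.1.2). The documents do not say whether sponsor staff see these results.

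**Working it through.** **Which analytes the rule covers**

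| Analyte | Post-dose samples | Withheld under Protocol 8.6? |
|---|---|---|
| Six lipid-panel analytes | Weeks 2, 4, 8, 12, ET | Yes |
| ApoB and other apolipoproteins, Lp(a) | Weeks 4, 8, 12, ET | Unclear: 8.6 can be read as including them; the objectives, Appendix A and SAP 9.3 list them separately |
| hsCRP, SAA, adiponectin, fibrinogen | Week 12, ET | No: listed as additional to the lipid parameters |

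Protocol 9.3.1.2 lists hsCRP endpoints at Weeks 4 and 8. The synopsis, Protocol 7, Appendix A and SAP 6.2 all have Week 12 only, so that line does not show an earlier hsCRP result.

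**When a released hsCRP result could matter.** The Week 12 visit is on Day 85 or up to 3 days earlier, and LDL-C and hsCRP are drawn at that same visit. Follow-up is on Day 113, so 113 - 85 = 28 days of adverse-event assessment remain. For a completer, no post-dose hsCRP result exists before the primary LDL-C sample is taken. A subject at the ET visit is already being withdrawn.

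**How informative one result is.** The plan states no figure for this. Under 1:1 allocation, with normally distributed changes, equal SDs and a cut-off midway between the arm means, the probability of a correct guess is Phi(d/2), where d is the difference between arms divided by the SD. The documents give neither an effect size nor an SD for hsCRP or ApoB, so d is an assumption:

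| Assumed d | Phi(d/2) | Correct guess |
|---|---|---|
| 0 | Phi(0) | 50% |
| 0.5 | Phi(0.25) | 60% |
| 0.85 | Phi(0.425) | 66% |
| 1.0 | Phi(0.5) | 69% |
| 1.5 | Phi(0.75) | 77% |
| 2.0 | Phi(1.0) | 84% |

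The 0.85 row borrows the LDL-C planning values in Protocol 9.1 (17/20 = 0.85). Those values reproduce the plan's own sample size: a two-sided 5% t-test with 80% power needs 22.7, so 23 evaluable per arm, and 23/0.90 = 25.6, so 26 randomized. Nothing in the documents says that ApoB or hsCRP shares this ratio.

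With two markers, each at d = 0.85 and with correlation r, the probability is Phi(sqrt(2 x 0.85^2/(1 + r))/2). It is 73% at r = 0 and 67% at r = 0.9, so a second marker adds little when the two are strongly correlated.

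**The case against.** The strongest reply is that the rule already covers ApoB. In 8.6 the phrase "In addition to these lipid parameters" comes straight after the panel and apolipoprotein sentences, so its natural reading takes in both. The section also speaks of a full lipid panel when it means the panel alone, while the exception uses a broader term. The SAP list "Baseline for lipids (ie, LDL-C, non-HDL-C, TC, TG, HDL-C and VLDL-C" was written to define baseline for analysis and does not instruct a laboratory. This stands to the extent that a reader who infers from SAP 9.3 that Week 4 and Week 8 ApoB results go to sites would be claiming more than the documents show. It does not settle the matter the other way, because a laboratory working from the Appendix A panel could send ApoB and still be following the text.

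A second reply is that the harm is small. hsCRP comes back only after treatment ends, most of the adverse-event period precedes it, and safety is summarized without statistical testing (Protocol 9.3.2). This also stands. A reader might infer that the release threatens the primary result or decisions to stop treatment. For hsCRP in completers the timing rules that out, and for ApoB it depends on a release that is not established.

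A third reply is that sites keep a treatment signal anyway: Protocol 1.3 reports small mean rises in creatinine and BUN within the first 2 to 4 weeks. That is true, and it limits the benefit of any change. It is a weak signal that safety monitoring needs, whereas the hsCRP result comes from the efficacy list. Finally, the documents cite no gemcabene effect on SAA, adiponectin or fibrinogen, so the case for withholding those three is simplicity of the rule rather than a known signal.

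**Conclusion.** The point holds as a minor gap in blinding. hsCRP and SAA are outside the exception, and hsCRP is described as markedly drug-responsive. Its release at Week 12 or ET leaves up to about four weeks in which adverse-event and relatedness judgments could be made with partial knowledge of the arm. Coverage of apolipoproteins is ambiguous; influence during the treatment period arises only if ApoB is in fact being released.

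One result would give a correct guess about 60% to 84% of the time across the assumed range of d, so the blind would be weakened and not broken. Those percentages rest wholly on assumed standardized differences, normality and equal spread. Sample size, power and type I error are unaffected.

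**What to change.** Reword the exception in Protocol 8.6 so that all post-randomization results for the efficacy parameters listed in Appendix B (lipid panel, apolipoproteins, Lp(a), hsCRP, SAA, adiponectin and fibrinogen) are withheld from sites and from blinded sponsor staff until unblinding. Referring to the Appendix B list removes the need to decide what counts as a lipid. State in the same sentence that all safety laboratory results continue to be released. Appendix B lists chemistry, hematology, coagulation and urinalysis apart from the efficacy parameters, so no listed safety result is lost.

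The cost is one protocol sentence and a change to the central laboratory's reporting setup. The weak signal from visible creatinine and BUN would remain.

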8.7 Vital Signs

Measurement of vital signs will include an assessment of pulse rate, blood pressure, respiration rate, and temperature. Vital signs will be measured at all study visits, excluding the Follow-up Visit. Blood pressure should be obtained in the seated position, after the subject has rested comfortably for at least 5 minutes. Blood pressure at the Screening Visit should be obtained in both arms and the arm with the highest value should be used for ongoing monitoring throughout the rest of the study. If an automated assessment is performed, the same machine should be used for the subject throughout the study when possible. Care should be taken to ensure an appropriate cuff size is utilized.

